7.6.1.2. Procedures for Eliciting and Recording Adverse Events

Investigator and study personnel will report all AEs and SAEs whether elicited during subject questioning, discovered during physical examination, laboratory testing and/or other means by recording them on the CRF and/or SAE form, as appropriate.

Eliciting Adverse Events

An open-ended or non-directed method of questioning should be used at each study visit to elicit the reporting of AEs.

Recording Adverse Events

The following information should be recorded on the Adverse Events and Pre-existing Conditions CRF:

- Description including onset and resolution dates
- Whether it met SAE criteria
- Severity
- Relationship to study treatment or other causality
- Outcome

Diagnosis vs. Signs or Symptoms

In general, the use of a unifying diagnosis is preferred to the listing out of individual symptoms. Grouping of symptoms into a diagnosis should only be done if each component sign and/or symptom is a medically confirmed component of a diagnosis as evidenced by standard medical textbooks. If any aspect of a sign or symptom does not fit into a classic pattern of the diagnosis, report the individual symptom as a separate AE.

Important exceptions for this study are adverse reactions associated with the infusion of LV. For IRRs, do not use the NCI CTCAE terms of “cytokine release syndrome,” “acute infusion reaction,” or “allergic or hypersensitivity reaction.” Instead, record each sign or symptom as an individual AE. If multiple signs or symptoms occur with a given infusion-related event, each sign or symptom should be recorded separately with its level of severity.

Recording Serious Adverse Events

For SAEs, record the event(s) on both the CRF and an SAE form.

The following should be considered when recording SAEs:

- Death is an outcome of an event. The event that resulted in the death should be recorded and reported on both an SAE form and CRF.
- For hospitalizations, surgical, or diagnostic procedures, the illness leading to the surgical or diagnostic procedure should be recorded as the SAE, not the procedure itself. The procedure should be captured in the narrative as part of the action taken in response to the illness.

Progression of the Underlying Malignancy

Since progression of underlying malignancy is being assessed as an efficacy variable, it should not be reported as an AE or SAE. The terms “Disease Progression”, “Progression of Disease”, or “Malignant disease progression” and other similar terms should not be used to describe an AE or SAE. However, clinical symptoms of progression may be reported as AEs or SAEs if the symptom cannot be determined as exclusively due to progression of the underlying malignancy or does not fit the expected pattern of progression for the disease under study. In addition, complications from progression of the underlying malignancy should be reported as AEs or SAEs.

Pregnancy

It is the responsibility of investigators or their designees to report any pregnancy or lactation (spontaneously reported to them) that occurs in a subject (or partner of a male subject) during the trial. If a subject becomes pregnant while on study, the site will contact the subject at least monthly and document the subject’s status until the pregnancy has been completed or terminated.

Pregnancies and lactations that occur after the consent form is signed but before treatment allocation must be reported by the investigator if they cause the subject to be excluded from the trial.

Notification to Drug Safety: Complete a Pregnancy Report Form for all pregnancies and lactations that occur from the time of treatment allocation until 6 months after the final dose of study drug, or 30 days following the last dose of study drug if the subject initiates new anticancer therapy, whichever is earlier. Include any pregnancies that occur in the partner of a male study subject. Only report pregnancies that occur in a male subject’s partner if the estimated date of conception is after the male subject’s first study drug dose. Email or fax to the sponsor’s Drug Safety Department within 24 hours of becoming aware of a pregnancy. All pregnancies will be monitored for the full duration; all perinatal and neonatal outcomes should be reported. Infants should be followed for a minimum of 8 weeks.

Collection of data on the CRF: All pregnancies (as described above) that occur within 30 days of the last dose of study drug will also be recorded on the Adverse Events and Pre-Existing Conditions CRF.

Pregnancy outcomes of spontaneous abortion, missed abortion, benign hydatidiform mole, blighted ovum, fetal death, intrauterine death, miscarriage, and stillbirth must be reported as

SAEs. Congenital anomalies or birth defects, as defined by the ‘serious’ criterion above (see definitions Section 7.6.1.1) should be reported as SAEs. Such events must be reported within 24 hours to the sponsor either by electronic media or paper. Electronic reporting procedures can be found in the electronic data capture data entry guidelines. Paper reporting procedures can be found in the Investigator Trial File Binder (or equivalent).

Potential Drug-Induced Liver Injury

The observation of the critical importance of altered liver function has been referred to informally as Hy’s Law (Reuben 2004). Hy’s Law can be used to estimate severity and the likelihood that a study drug may cause an increased incidence of severe hepatotoxicity.

The absence of hepatotoxicity in clinical trials provides a limited predictive value for potential hepatotoxicity in the clinical setting(s) being studied. However, finding 1 Hy’s Law case in clinical trials is ominous; finding 2 cases is highly predictive of a potential for severe drug-induced liver injury (DILI).

Definition

Briefly, potential Hy’s Law cases include the following 3 components:

1. Aminotransferase (ALT and/or AST) elevation $>3 \times$ ULN
AND
2. Total bilirubin $>2 \times$ ULN, without initial findings of cholestasis (i.e., elevated serum alkaline phosphatase),
AND

No other immediately apparent possible causes of aminotransferase elevation and hyperbilirubinemia, including, but not limited to, viral hepatitis, pre-existing chronic or acute liver disease, or the administration of other drug(s) known to be hepatotoxic.

Reporting Requirements

Any potential Hy’s Law case should be handled as a suspected unexpected serious adverse reaction (SUSAR) associated with the use of the drug and reported promptly to the sponsor.

Reporting should include all available information and should initiate close follow-up until complete resolution of the problem and completion of all attempts to obtain supplementary data.

Follow-up for Abnormal Laboratory Results Suggesting Potential DILI

In general, an increase of serum ALT or AST to $>3 \times$ ULN should be followed by repeat testing within 48 to 72 hours of serum ALT, AST, alkaline phosphatase, and total bilirubin, to confirm the abnormalities and to determine whether they are worsening.

Appropriate medical assessment should be initiated to investigate potential confounding factors and alternative causes of hepatotoxicity. During this investigation, consider holding study drug.

The guidance documents below are included in the study binder.

- FDA Guidance for Industry, Drug-Induced Liver Injury: Premarketing Clinical Evaluation, 2009.
- Health Canada Guidance Document; Pre-market Evaluation of Hepatotoxicity in Health Products, 2012.

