7.6.1.5. Sponsor Safety Reporting to Regulatory Authorities

Investigators are required to report all SAEs, including anticipated SAEs, to the sponsor (see Section [7.6.1.4](#)).

The sponsor will report all SAEs, including SUSARs, to regulatory authorities as required per local legislation or regulatory reporting requirements.

In the US, endpoints that assess disease-related mortality or major morbidity, as well as other SAEs that are not study endpoints but are known consequences of the underlying disease or condition that are anticipated to occur in the study population, should not be reported to the FDA as individual IND safety reports per the final rule amending the IND safety reporting requirements under 21 CFR 312.32 and the FDA's guidance Safety Assessment for IND Safety Reporting Guidance for Industry (draft guidance December 2015).

In this study, the SAEs that do not require individual IND safety reports to the FDA are progression of the underlying cancer. These anticipated SAEs will be reviewed periodically by the Seagen Drug Safety Department. If upon review, an SAE is occurring at a higher rate than that which would be expected for the study population, then an IND safety report for the SAE will be submitted to the FDA.

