9.3.8.3. Deaths and Serious Adverse Events

SAEs will be listed and summarized in the same manner as all AEs. Events with a fatal outcome will be listed.

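### Protocol 7.6.1.2 keeps disease progression off the AE/SAE forms, yet 7.6.1.5 makes progression the anticipated SAE whose rate is reviewed, and names no other data source for that review

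*Protocol*

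**What the plan says.** Protocol 7.6.1.2, under the progression subheading, is directed at sites: "Since progression of underlying malignancy is being assessed as an efficacy variable, it should not be reported as an AE or SAE". It adds that progression terms "should not be used to describe an AE or SAE". Two neighbouring classes are treated differently. Symptoms are optional and conditional: "clinical symptoms of progression may be reported as AEs or SAEs if the symptom cannot be determined as exclusively due to progression" (or if they do not fit the expected pattern). Complications are not optional: "complications from progression of the underlying malignancy should be reported as AEs or SAEs".

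Protocol 7.6.1.5 first sets the duty: "Investigators are required to report all SAEs, including anticipated SAEs, to the sponsor". It then identifies the anticipated class: "In this study, the SAEs that do not require individual IND safety reports to the FDA are progression of the underlying cancer". The sentences that follow have Drug Safety review these events periodically and send an IND safety report to the FDA if one occurs at a higher rate than expected for the population.

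On deaths, an earlier part of 7.6.1.2 says: "The event that resulted in the death should be recorded and reported on both an SAE form and CRF". Protocol 9.3.8.3 says: "Events with a fatal outcome will be listed". SAP 6.6.1 summarises and lists AEs that led to death. SAP 6.6.3 separately summarises total deaths, their timing relative to last treatment, relationship to disease and cause.

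**The concern.** A rate-based safety rule needs a numerator. The rule in 7.6.1.5 is defined over SAEs of one named type, and 7.6.1.2 tells sites not to submit that type. If sites comply, the rule cannot work as written, because nothing will be counted however often serious progression occurs.

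Deaths raise a related, weaker question. A site with a death due solely to progression finds one sentence asking for the causal event on an SAE form and, shortly afterwards, a paragraph saying that this event is not an AE or SAE. Sites that resolve this differently would send different records into the fatal-event listing and the SAP outputs on AEs that led to death.

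**Working it through.** No planned figure is in dispute, so the check is mainly a comparison of text.

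**Step 1. What reaches Drug Safety as an SAE, by type of event**

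| Event | Progression paragraph of 7.6.1.2 | What 7.6.1.5, or the death sentence of 7.6.1.2, expects |
|---|---|---|
| Progression itself | Not reported; terms barred | 7.6.1.5: named as the anticipated SAE, reported and rate-reviewed |
| Symptom exclusively due to progression and of the expected pattern | Outside the reporting exception | 7.6.1.5: not mentioned |
| Other symptom of progression | Optional | 7.6.1.5: not mentioned |
| Complication of progression | Reported under its own term | 7.6.1.5: not named |
| Death due solely to progression | Cause is not an AE or SAE | Death sentence: causal event goes on SAE form and CRF |

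**Step 2. What the review can count.** If sites follow 7.6.1.2, the number of progression SAEs received is 0 at any true rate. This needs no assumption beyond compliance. Complications do arrive, but no text groups them as progression-related for a rate. Progression is also captured as efficacy data, but no text says that the review uses it. Section 7.6.1.5 gives no expected rate either.

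**Step 3. Outputs affected.** Fatal AE/SAE records feed the listing in Protocol 9.3.8.3 and the outputs in SAP 6.6.1 on AEs that led to death. Total deaths and relationship to disease (SAP 6.6.3) and OS (Protocol 9.2.6, SAP 6.5.2.4) do not depend on whether the cause was entered as an SAE.

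**Step 4. Illustration of the death ambiguity.** Inputs: n = 30 per cohort or arm (Protocol 9.1); 90% exact Clopper-Pearson intervals, the plan's own method. Assumption, not from the documents: 3 subjects (range 2 to 6) die solely of progression within the reporting period, with no reportable complication, no other fatal AE, and every site following the same reading.

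- Progression paragraph followed: 0/30 = 0%. Upper limit 1 − 0.05^(1/30) = 9.5%, so the interval is 0% to 9.5%.
- Death sentence followed: 3/30 = 10%, interval 2.8% to 23.9%. This reproduces the protocol's own row for 10% at N = 30 (3%, 24%).
- Across the assumed range, the second figure runs from 2/30 = 6.7% to 6/30 = 20%.

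Mixed practice would fall between the two readings. Total deaths are the same under either.

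**The case against.** The strongest reply is that 7.6.1.5 is loosely worded and means serious consequences of progression. Its preceding paragraph covers SAEs that are known consequences of the disease, and 7.6.1.2 does require complications to be reported. That may be the intent, and it is right that complications reach Drug Safety. But the study-specific sentence names progression itself. The same preceding paragraph also covers study endpoints, and progression is a component of one (PFS). Even on this reading, no rule says which complications count towards the rate.

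On deaths, the progression paragraph can fairly be read as the specific rule limiting the general one, since the fatal criterion for an SAE in 7.6.1.1 presupposes an AE. That stands. The missing exception is therefore a source of possible variation, not a second outright contradiction. CRF completion guidelines or the study manual may settle it, but they are not among the documents.

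A reader might infer three stronger things that the documents do not support:

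- **That this is the sponsor's only safeguard.** Protocol 7.6 provides real-time review of SAEs. Section 9.3.9 provides continuous benefit-risk monitoring and looks at PFS and OS at the interim analyses, which are planned for Parts A and B. What may fail as worded is one IND-reporting clause.
- **That death counts in general are unreliable.** Only fatal AE/SAE records are exposed (Step 3).
- **That SAE rates cannot be compared between cohorts or arms.** Nothing shows that site practice follows cohort or arm, Part C is randomized, and no multiple comparisons are planned. The reporting period is longer in Part C Arms 2 and 3 (to 90 days after last treatment, against 30 days for monotherapy, or to the end-of-treatment visit if later), so an unequal effect is possible. It is not demonstrated.

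**Conclusion.** The point holds as an inconsistency in current protocol text. If sites follow 7.6.1.2, the excess-rate review in 7.6.1.5 receives zero progression SAEs, and no alternative source is named. Separately, fatal AE/SAE outputs may vary with how sites read 7.6.1.2. The contrast of 0/30 with 3/30 shows the direction of that effect only. It rests on an assumed count and uniform site practice, and it should not be scaled to the whole study, because the documents give no rate of death from progression and the enrollment total is a ceiling. The primary endpoint, OS, total deaths and relationship to disease are untouched. The consequence is moderate and the correction is cheap, so it should be made.

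**What to change.** Put both sections of the protocol and the SAP under one rule.

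- **Protocol 7.6.1.2:** keep progression off the AE/SAE forms. State, as an explicit exception to the sentence on deaths, that a death due solely to progression is recorded as death and disease-assessment data and not as an SAE.
- **Protocol 7.6.1.5:** base the periodic excess-rate review on the progression and death data already collected, by cohort or arm. Limit the anticipated SAEs to the reportable complications of progression. The same edit should say where the expected rate comes from.
- **SAP 6.6.1:** apply the same rule to the table and listing of AEs that led to death.

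The cost is protocol and SAP wording, plus a periodic clinical-database extract for Drug Safety, which is the one real burden. Tumor assessments, survival follow-up and the death summary in SAP 6.6.3 already call for the underlying data. The documents do not name the form that holds death data, so the sponsor should confirm where it is recorded. Visits, treatment and sample size do not change.

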7.6.1.3. Reporting Periods for Adverse Events and Serious Adverse Events

For LV monotherapy (Part A, Part B, Part C Arm 1), the safety reporting period for all AEs and SAEs is from study Day 1 (predose) through the EOT visit or 30 days after the last study treatment, whichever is later. For pembrolizumab and LV combination therapy (Part C Arms 2 and 3), the reporting period for all AEs and SAEs is from study Day 1 (predose) through the EOT visit or 90 days after the last study treatment, whichever is later. However, all study protocol-related AEs are to be recorded from the time of informed consent. All SAEs that occur after the safety reporting period and are considered study treatment-related in the opinion of the investigator should also be reported to the sponsor.

SAEs will be followed until significant changes return to baseline, the event stabilizes (recovering/resolving) or is no longer considered clinically significant by the investigator, or the subject dies or withdraws consent. All non-serious AEs will be followed through the safety reporting period. Certain non-serious AEs of interest may be followed until resolution, return to baseline, or study closure. In particular, these include AEs of peripheral neuropathy in all subjects.

7.6.1.4. Serious Adverse Events Require Immediate Reporting

Within 24 hours of observing or learning of an SAE, investigators are to report the event to the sponsor, regardless of the relationship of the event to the study treatment regimen.

For initial SAE reports, available case details are to be recorded on an SAE form. At a minimum, the following should be included:

- Subject number
- Date of event onset
- Description of the event

Study treatment, if known

The completed SAE form and SAE Fax Cover Sheet are to be emailed or faxed to the sponsor's Drug Safety Department within 24 hours (see email or fax number specified on the SAE report form).

Relevant follow-up information is to be submitted to the sponsor as soon as it becomes available.

7.6.1.5. Sponsor Safety Reporting to Regulatory Authorities

Investigators are required to report all SAEs, including anticipated SAEs, to the sponsor (see Section [7.6.1.4](#)).

The sponsor will report all SAEs, including SUSARs, to regulatory authorities as required per local legislation or regulatory reporting requirements.

In the US, endpoints that assess disease-related mortality or major morbidity, as well as other SAEs that are not study endpoints but are known consequences of the underlying disease or condition that are anticipated to occur in the study population, should not be reported to the FDA as individual IND safety reports per the final rule amending the IND safety reporting requirements under 21 CFR 312.32 and the FDA's guidance Safety Assessment for IND Safety Reporting Guidance for Industry (draft guidance December 2015).

In this study, the SAEs that do not require individual IND safety reports to the FDA are progression of the underlying cancer. These anticipated SAEs will be reviewed periodically by the Seagen Drug Safety Department. If upon review, an SAE is occurring at a higher rate than that which would be expected for the study population, then an IND safety report for the SAE will be submitted to the FDA.

7.6.1.6. Events of Clinical Interest

Selected non-serious and serious AEs are also known as Events of Clinical Interest (ECIs) and must be reported to the Sponsor within 24 hours of awareness.

ECIs for this trial include:

1. An overdose of either study product, as defined in Section 5.5.2, and is not associated with clinical symptoms or abnormal laboratory results.
2. An elevated AST or ALT lab value that is ≥ 3 x ULN, and an elevated total bilirubin lab value that is ≥ 2 x ULN and, at the same time, an alkaline phosphatase lab value that is < 2 x ULN, as determined by way of protocol-specified laboratory testing, or unscheduled laboratory testing.*

*Note: These criteria are based upon available regulatory guidance documents. The purpose of the criteria is to specify a threshold of abnormal hepatic tests that may require an additional evaluation for an underlying etiology. The trial site guidance for assessment and follow-up of these criteria can be found in the Investigator Trial File Binder (or equivalent). It may also be appropriate to conduct additional evaluation for an underlying etiology in the setting of abnormalities of liver blood tests including AST, ALT, bilirubin, and alkaline phosphatase that do not meet the criteria noted above. In these cases, the decision to proceed with additional evaluation will be made through consultation between the study investigators and the medical monitor. However, abnormalities of liver blood tests that do not meet the criteria noted above are not ECIs for this trial.

7.6.2. Vital Signs

Vital sign measurements are to include heart rate, systolic and diastolic blood pressure, and temperature. All vital signs should be measured after the subject has been sitting/resting.

Part A: Vital signs will be measured on Day 1 of each cycle and recorded within 60 minutes prior to the start of LV infusion and within 30 minutes after completion of LV infusion.

Part B: Vital signs will be measured on Day 1, Day 8, and Day 15 of each cycle and recorded within 60 minutes prior to the start of LV infusion and within 30 minutes after completion of LV infusion.

Part C: Vital signs will be measured on Day 1 and Day 8 of each cycle in Arm 1 and Arm 2, or on Day 1, Day 8, and Day 15 of each cycle in Arm 3. Vital signs will be recorded within 60 minutes prior to the start of LV infusion, within 30 minutes after completion of LV infusion, and during infusion as clinically indicated (Arm 1). Vital signs should be measured within 60 minutes prior to LV infusion, within 60 minutes prior to pembrolizumab infusion (Day 1 only), within 2 hours of ending each infusion, and during infusion(s) as clinically indicated (Arm 2 and Arm 3).

7.6.3. Clinical Laboratory Tests

The following safety laboratory assessments will be performed by local laboratories at the designated time points (see [Appendix A](#), [Appendix B](#), [Appendix C](#), and [Appendix D](#)) during the course of the study. Results of all clinical laboratory tests except pregnancy and PSA tests are to be submitted to iRIS. Instructions for submission to iRIS are located in the iRIS Manual.

- Serum chemistry panel: including sodium, potassium, blood urea nitrogen/blood urea, creatinine, calcium, albumin, and magnesium.
- Liver function tests including total bilirubin, alkaline phosphatase, ALT, and AST
- CBC with differential: white blood count, hemoglobin, hematocrit and platelets; and the differential including, but not limited to, neutrophils, lymphocytes, and monocytes
- PSA test (prostate cancer patients only)
- Testosterone measurement (at Screening, prostate cancer patients only)
- Blood glucose
 - Fasting blood glucose is only required at screening. If fasting blood glucose is elevated, a repeat assessment must be obtained.
- HbA1c: if HbA1c is elevated during screening, HbA1c assessment must be repeated to confirm
- The estimated GFR should be calculated using the MDRD equation as applicable, with serum creatinine (Scr) reported in mg/dL.

$$\text{GFR (mL/min/1.73 m}^2\text{)} = 175 \times (\text{Scr})^{-1.154} \times (\text{Age})^{-0.203} \times (0.742 \text{ if female}) \times (1.212 \text{ if African American})$$

- Thyroid function tests, including TSH, T3 or free T3, and free T4 (Part C Arm 2 and Arm 3).

